9.1. EXTENT OF EXPOSURE

Study drug exposure will include:

- Treatment duration by treatment arm
- Total dose received by treatment arm

Treatment duration (in weeks) is calculated as (the date of the last dose of study drug - the date of the first dose of study drug + 1) / 7 and rounded to 1 decimal place.

Total dose taken will be calculated as number of tablets/capsules dispensed - number of tablets/capsules, including all doses for glimepiride, returned. For unreturned bottles, if subject has completed the study, all study medications are considered as completely taken. If a subject withdrew early, and it is not the last kit dispensed, or if 2 kits are dispensed and only one is not returned, all medications will be considered as completely taken. If a subject withdrew early, and all kits dispensed are the last visit are not returned, the number taken is considered as what expected from date of dispense to the date of last dose date. Summary statistics for total dose taken will be provided by treatment group for the double-blind treatment period.

Summary statistics for treatment duration (in weeks) and total dose received, as well as a frequency summary of treatment duration categories (e.g., < 1, 1 - < 6 weeks), will be provided. Summary will also be conducted for subjects who have been prescribed insulin or sulfonylurea to control their diabetes.

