5.9.2 Investigational Product Kit

Each kit contains 1 bottle of 90 tablets of bexagliflozin tablets, 20 mg or placebo.

The labels attached to each study kit will contain some or all of the following information: the kit number, protocol number, product identification, blinded batch number, subject number, storage conditions, sponsor's name, manufacturer's name and address, investigator's name, expiration date, and the investigational drug caution statement.

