6.8 Dispensing Investigational Product

Each study subject will receive one bottle of run-in drug on visit V2 and one bottle of investigational product every 12 weeks between week 1 and 48. Each subject will receive two bottles of investigational product every 24 weeks after week 48.

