7.5 Discontinuation of Investigational Product Administration

Subjects who discontinue the investigational product administration early but are willing to remain in the study to allow safety information to be collected should complete the End of Treatment visit procedures. Safety data may be documented following the scheduled clinic visit and/or phone interview procedures as much as possible without the study drug

dispensation and accountability procedures. Alternative follow up methods to allow safety assessment to be recorded may be implemented as unscheduled visits.

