5.5. PROTOCOL DEVIATIONS

Protocol deviations will be captured during monitoring visits. Major protocol deviations that could affect the primary and secondary variables, in the opinion of the medical monitor, will be considered when determining a subject's eligibility for the PP population. Table 5 describes some possible types of major protocol deviations. All protocol deviations will be reviewed and determined as major or minor before database lock.

Table 5 Some Possible Types of Major Protocol Deviations

Category	Criteria	Exclusion
Inclusion/Exclusion Criteria		
Ineligible subject is enrolled	- Subjects not satisfying HbA _{1c} inclusion criteria - Treated with SGLT2 within 3 months of screening	Subject exclusion
Prior or Concomitant Medication Restrictions		
Use of another SGLT2 inhibitor	Use of an SGLT2 inhibitor as the rescue medication for hyperglycemia	Visit exclusion [exclude data post SGLT2 starts]
Dosing Non-Compliance		
Dosing Non-Compliance	-Subject missed more than 50% of the investigational product doses between week 12 and week 24	Subject exclusion

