9.2. TREATMENT COMPLIANCE

Subjects will be provided with dosing instructions each time study medication is dispensed. Subjects will also be instructed to bring their medication with them to every visit. During the run-in period, subjects will be considered compliant in investigational product administration by missing no more than one dose of run-in medication. Subjects who are not compliant during the run-in period will be excluded from randomization.

At each visit the study staff will review the self-monitored blood glucose (SMBG) diary and medication use with the subject and record the drug consumption in the CRF. Reasons for non-adherence will also be recorded in the protocol deviation log if applicable.

Compliance in the double-blind phase is calculated for as follows:

- Percent compliance = (number of tablets taken / number of tablets that should have been taken) x 100.
- Number of tablets taken = number of tablets dispensed - number of tablets returned.

- Number of tablets that should have been taken = number of exposure days.
- Number of exposure days = last dose date - first dose date + 1.

Summary statistics for tablet compliance (%) will be provided by treatment arm for the double-blind treatment period. A frequency summary of compliance will also be presented with the following categories: < 75%, 75-<100%, 100-120%, and > 120%. Summary will also be conducted for subjects who have been prescribed insulin or sulfonylurea to control their diabetes.

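### Crediting unreturned bottles in full to study completers lets total dose and percent compliance exceed one tablet a day

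*Combined protocol and SAP*

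**What the plan says.** SAP section 9.1 computes total dose as tablets dispensed minus tablets returned, and then deals with bottles that never come back in three ways.

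- **Study completers:** "For unreturned bottles, if subject has completed the study, all study medications are considered as completely taken".
- **Early withdrawals, partial non-return:** a missing kit is also counted as fully taken if it was not the last one dispensed, or if two were dispensed and only one is missing.
- **Early withdrawals with every kit from the last visit missing:** only here is the credit limited to the doses expected between dispensing and the last dose date.

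The same sentence on total dose also mentions capsules and has the words "including all doses for glimepiride, returned". SAP section 3.9 and protocol section 5.1.1 list only bexagliflozin 20 mg tablets and placebo tablets.

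SAP section 9.2 takes percent compliance as tablets taken over tablets due. The denominator is "Number of tablets that should have been taken = number of exposure days", where exposure days run from first to last dose inclusive. The result is reported as a mean and in four bands: < 75%, 75-<100%, 100-120% and > 120%.

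SAP Table 5 (section 5.5) lists this dosing deviation as a ground for exclusion from the Per Protocol set: "Subject missed more than 50% of the investigational product doses between week 12 and week 24". It names no data source.

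Protocol section 7.5 provides for "Subjects who discontinue the investigational product administration early but are willing to remain in the study", and SAP section 7.1 reports completing the study and completing study drug as separate dispositions.

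**The concern.** The numerator and denominator of compliance follow different clocks. The denominator stops at the last dose. For a completer, the numerator includes every tablet in a lost bottle, even tablets that could only have been taken after the last dose at one a day. Two subjects with the same last dose date and the same lost last kit therefore get different credit, depending only on whether they later completed follow-up. The SAP gives no reason for this.

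The design makes such cases foreseeable. Treatment ends for everyone on an event-driven trigger (protocol section 6.12), so completers finish at arbitrary points in their last dispensing cycle. After week 48 that cycle holds 180 tablets.

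At stake are the total-dose summary, mean compliance and the compliance bands. Membership of the Per Protocol set is also at stake if tablet counts decide the Table 5 deviation. That set supports the primary endpoint (SAP section 8.1.1) and repeats the key secondary analyses (section 8.2.1).

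**Working it through.** The documents give no compliance figure to reproduce, so the check applies sections 9.1 and 9.2 to single subjects.

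**Inputs**
- Bottle size: "Each kit contains 1 bottle of 90 tablets of bexagliflozin tablets, 20 mg or placebo" (protocol section 5.9.2).
- Supply to week 48: "one bottle of investigational product every 12 weeks between week 1 and 48", so 90 tablets per 84 days (protocol section 6.8).
- Supply later: "Each subject will receive two bottles of investigational product every 24 weeks after week 48", so 180 tablets per 168 days (same section).
- Dose: one tablet a day (protocol section 5.3).
- Compliance = (dispensed − returned, with the 9.1 credit for lost bottles) ÷ (last dose date − first dose date + 1).

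Day 1 is the first dose. Dispensing falls exactly on schedule, and unused tablets in other bottles are returned.

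**Case 1: drug stopped at week 14 (Day 98), study completed, week-12 bottle lost.**
- First bottle returned with 6 left: 90 − 6 = 84 taken.
- Lost bottle: 90 credited.
- Compliance = (84 + 90)/98 = 174/98 = 177.6%.
- At one tablet a day, at most 98 were possible.

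**Case 2: adherent completer, treatment ends 14 days after the week-96 dispensing, both bottles lost.**
- To week 96: 672 tablets in 672 days. Lost pair: 180 credited. Exposure: 672 + 14 = 686 days.
- Compliance = (672 + 180)/686 = 852/686 = 124.2%, in the > 120% band.

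**Case 3: as case 2, with 50% adherence up to week 96.**
- Compliance = (336 + 180)/686 = 516/686 = 75.2%, in the 75-<100% band.
- Even if all 14 final doses were taken, the count is 350/686 = 51.0%, in the < 75% band.

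**Case 4: early withdrawal, adherent, last dose 14 days after the week-96 dispensing, one of the two bottles returned full and the other lost.**
- Compliance = (672 + 90)/686 = 762/686 = 111.1%. Had both been lost, the early-withdrawal limit would give (672 + 14)/686 = 100%. Returning a full bottle raises the score.

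**Case 5: one mid-study bottle lost, subject on drug throughout and adherent.**
- The credit adds 90 − 84 = 6 tablets.
- At 52 weeks: 370/364 = 101.6%. At 104 weeks: 734/728 = 100.8%.

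**Weeks 12 to 24 in case 1.**
- Due: 84. Possible before the stop: 14. Missed: 70/84 = 83.3%, above the 50% limit in Table 5.
- On the 9.1 credit, 90 are counted against 84 due, so none appear missed.
- The same reversal occurs for any stop after the week-12 dispensing and before Day 84 + 42 = 126, if that bottle is lost and the study completed.

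These cases are illustrations and not bounds. With the week-12 bottle lost, a stop on Day 85 gives 174/85 = 204.7%.

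**The case against.** The strongest reply is that little depends on these counts. Total dose and compliance are descriptive. The primary ITT analysis and the ITT key secondary analyses do not use tablets. Treatment duration uses dose dates, the imputation subgroup uses completion of 24 weeks of treatment, and event rates use time to end of study. All of this stands, and it limits the weight of the point.

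Three stronger readings are tempting, and the documents do not support them.

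- A reader might infer that one lost bottle scores 90/84 = 107%. That uses a 12-week denominator. Section 9.2 defines one figure over the whole double-blind period, so the effect is that of case 5, which leaves an adherent subject in the 100-120% band.
- A reader might infer that the week-14 stopper appears dosed through week 24. This is true of the tablet count only. The last dose date is recorded at the End of Treatment visit (protocol section 7.3.11), treatment duration would read 14.0 weeks, and disposition separately reports completion of drug through week 24.
- A reader might infer that the Per Protocol estimate is diluted. Nothing ties Table 5 to the 9.1 credit. Deviations are captured at monitoring visits and classified before database lock, and drug consumption is recorded in the CRF at each visit. The effect is conditional.

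The documents also say nothing about how often bottles are lost, or whether loss goes with poor adherence, so no arm-level effect can be estimated.

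The reply does not justify the rule itself. It is stated explicitly, it yields values that the recorded dates rule out at one tablet a day, and it contradicts the limit that the SAP itself applies to some early withdrawals.

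**Conclusion.** The point holds as a limited error of derivation and should be corrected. Under section 9.1, a completer who stopped drug early, or whose treatment ended soon after a dispensing, can be credited with tablets that could not have been taken at one a day. The worked cases give 178% and 124%. In a third, a half-adherent subject is lifted out of the lowest band (75.2% against at most 51.0%). Early withdrawals who return one of two kits are affected too (111.1% in case 4).

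The conclusion rests on the 9.1 credit carrying into the 9.2 numerator. For completers this hardly matters, because dispensed minus returned gives the same count when nothing comes back.

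The impact is confined to the exposure and compliance summaries and, if Table 5 is scored from these counts, to the secondary Per Protocol set. How many subjects would be affected cannot be derived from the documents.

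**What to change.** For all subjects, completers included, cap the tablets credited from unreturned bottles **per dispensing visit**. The cap is the number of days from that dispensing to the earlier of the next dispensing or the last dose date, minus tablets taken from any returned bottle of the same dispensing, with a floor of zero. Use this count for total dose and percent compliance.

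With this cap:
- Case 1 becomes (84 + 14)/98 = 100%.
- Cases 2 and 4 become (672 + 14)/686 = 100%.
- Case 3 becomes 350/686 = 51.0%.

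A cap per bottle would not do. With two bottles dispensed together it would credit 14 + 14 tablets for 14 days in case 2, giving 700/686 = 102.0%.

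Three further changes are needed:
- **Table 5:** base the week 12-24 criterion on the capped count together with the last dose date, so that days after the last dose count as missed. The 9.2 percentage alone cannot show this, since its denominator ends at the last dose.
- **Non-return:** report by arm the number of subjects with any unreturned bottle. The cap still assumes full adherence while on drug, and readers need to see how much rests on that.
- **Stray text:** delete the references to capsules and glimepiride from section 9.1.

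The cost is a small change of SAP wording and programming. The last dose date is already recorded, and the existing early-withdrawal rule already relies on dispensing dates. Reported compliance may look slightly lower.

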9.2. TREATMENT COMPLIANCE

Subjects will be provided with dosing instructions each time study medication is dispensed. Subjects will also be instructed to bring their medication with them to every visit. During the run-in period, subjects will be considered compliant in investigational product administration by missing no more than one dose of run-in medication. Subjects who are not compliant during the run-in period will be excluded from randomization.

At each visit the study staff will review the self-monitored blood glucose (SMBG) diary and medication use with the subject and record the drug consumption in the CRF. Reasons for non-adherence will also be recorded in the protocol deviation log if applicable.

Compliance in the double-blind phase is calculated for as follows:

- Percent compliance = (number of tablets taken / number of tablets that should have been taken) x 100.
- Number of tablets taken = number of tablets dispensed - number of tablets returned.

- Number of tablets that should have been taken = number of exposure days.
- Number of exposure days = last dose date - first dose date + 1.

Summary statistics for tablet compliance (%) will be provided by treatment arm for the double-blind treatment period. A frequency summary of compliance will also be presented with the following categories: < 75%, 75-<100%, 100-120%, and > 120%. Summary will also be conducted for subjects who have been prescribed insulin or sulfonylurea to control their diabetes.

9.3. ADVERSE EVENTS

Adverse events will be collected and recorded from the time a subject signs the informed consent form (ICF) to the last scheduled contact. Any new serious adverse event (SAE) reported by the subject to the investigator that occur after the last scheduled contact, and are determined by the investigator to be reasonably associated with the use of the investigational product, should be reported to the sponsor or designated personnel. This may include SAEs that are captured on follow-up telephone contact or at any other time point after the defined study period (i.e., up to last scheduled contact). The investigator should follow SAEs identified after the last scheduled contact until the events are resolved, or the subject is lost to follow-up. The investigator should continue to report any significant follow-up information to the sponsor until the event has been resolved. This study requires that subjects be actively monitored for SAEs for at least 4 weeks after the last treatment.

For all AEs, preferred AE terms and system organ class (SOC) will be coded using terminology from the Medical Dictionary for Regulatory Activities (MedDRA), version 18.1.

A treatment-emergent adverse event (TEAE) is defined as an AE that begins after the first administration of double-blind study medication or an existing AE that worsens after the first dose of double-blind study medication. All reported AEs will be listed, but only TEAEs will be summarized in tables.

Drug-related AEs will be considered those to be possibly, probably and definitely related to bexagliflozin administration based on the investigators' assessment.

Unless otherwise specified, AEs will be summarized by SOC and PT, with SOC and PTs within SOC presented in descending order of subject incidence.

9.3.1. Derived Data

AE onset day is calculated as (date of AE start - date of double-blind first dose + 1). The onset day will be missing if the start date is missing or partially missing.

9.3.2. Data Summarization

AE summary tables are listed below:

- An overall summary of the number and percentage of subjects reporting any TEAEs, serious TEAEs, treatment-related TEAEs, serious treatment-related TEAE, any TEAEs leading to treatment discontinuation, any TEAEs leading to subject discontinuation and TEAEs leading to death.
- TEAEs overall and by SOC and PT
- TEAEs by severity, overall and by SOC and PT
- Serious TEAEs, overall and by system organ class and preferred term
- TEAEs by relationship to study treatment, overall and by system organ class and preferred term
- TEAEs leading to treatment discontinuation, overall and by SOC and PT
- TEAEs leading to study discontinuation, overall and by SOC and PT
- Most common TEAEs. Most common TEAEs are defined as TEAEs that occur in > 3% of the subjects in either of the treatment arms.

For summary tables, subjects having more than 1 event with the same PT will be counted once for that term. Subjects having more than 1 event with the same SOC will be counted once for each event and once for that SOC. For tabulations by severity, only a subject's most severe event within the category (e.g. overall, SOC, PT) will be counted; similarly, for tabulations by relationship, only a subject's most related event within a category will be counted. The denominator for percentages will be the number of subjects in the Safety Analysis Set for the given treatment arm (i.e., the N's for the columns).

Table below will also be presented for subjects who have been prescribed insulin or sulfonylurea to control their diabetes:

- An overall summary of the number and percentage of subjects reporting any TEAEs, serious TEAEs, treatment-related TEAEs, serious treatment-related TEAE, any TEAEs leading to treatment discontinuation, any TEAEs leading to subject discontinuation and TEAEs leading to death.
- TEAEs overall and by SOC and PT
- Serious TEAEs, overall and by system organ class and preferred term
- TEAEs leading to treatment discontinuation, overall and by SOC and PT
- TEAEs leading to study discontinuation, overall and by SOC and PT.

Listings will be provided for all AEs and the following subsets:

- Serious AEs
- AEs leading to treatment discontinuation
- AEs leading to death.

AE leading to treatment discontinuation and death will be presented for subjects who have been prescribed insulin or sulfonylurea to control their diabetes.

9.3.3. AE of Special Interest

AEs of special interest include UTI, pyelonephritis urosepsis, GMI, diuretic effects including hypovolemia, hypotension episodes, hypoglycemia, hepatotoxicity, cardiovascular events, fractures, malignancies, hypersensitivity reactions, acid-base disorders including diabetic ketoacidosis (DKA), rash, and renal failure events. These AEs of special interest, except for DKA, cardiovascular events and amputations, will be prospectively identified based on the MedDRA PTs in the AEs log by a medical expert prior to the data base lock and unblinding of the individual subject treatment assignment. The list of AEs of special interest will be confirmed in a peer review process. Cardiovascular events and DKA will be adjudicated and the confirmed MACE events (See Section 9.3.3.3), and confirmed or possible DKA events (See Section 9.3.3.5) will be summarized in the same AE of special interest table. The hypoglycemia events by severity, and amputations will be summarized separately.

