9.6.4 Other Safety Endpoints

The other safety endpoints include

- Time to a 5-point composite adjudicated endpoint of CV death, non-fatal MI, non-fatal stroke, hospitalization for unstable angina, or coronary revascularization
- Time-to a 6-point composite adjudicated endpoint of CV death, non-fatal MI, non-fatal stroke, hospitalization for unstable angina, hospitalization for heart failure, and coronary revascularization; and time to onset of event
- Time to individual events including all-cause mortality, CV death, non-fatal MI, non-fatal stroke, transient ischemic attack, hospitalization for unstable angina, hospitalization for heart failure, and coronary revascularization; and time to onset of each event
- Incidence of treatment emergent AEs (TEAEs) of interest
- Incidence of amputations
- Change from baseline in eGFR by study visit
- Change from baseline in UACR by study visit

AEs of special interest include the following categories:

- Genital mycotic infections
- Urinary tract infections including urosepsis and pyelonephritis
- Diuretic effects including hypovolemia
- Hypotension episodes
- Hepatotoxicity
- Hypoglycemia
- Falls and fractures
- Malignancies

- Hypersensitivity reactions
- Acid-base disorders including DKA
- Renal failure events

AEs of special interest will be defined programmatically based on MedDRA system organ class and preferred terms which will be predefined by a blinded medical reviewer and will be specified in the Statistical Analysis Plan.

Event terms, signs, and symptoms will be documented in the listings. The number and percentage of subjects who have experienced treatment emergent adverse events (TEAEs) of special interest will be summarized for each treatment group by type of AE. A TEAE is an AE that started or worsened in severity at or after start of randomized treatment.

A case report form for adverse events that require amputation will be completed to capture the date and type of procedure, anatomic location, and causes. The number and percentage of subjects experienced any TEAE that requires amputation will be summarized for each treatment group by type of events. The incidence of lower extremity amputation per 100 patient years will also be summarized. Additional analyses will be specified in the statistical analysis plan to evaluate potential risks in subpopulations based on age, gender, or other baseline characteristics (if sample size allows).

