2.1. RESPONSIBILITIES

Theracos has designed the study protocol and is responsible for the conduct of the study. Covance is responsible for the development and validation of a clinical database using the MediData RAVE platform.

INC Research will perform the statistical analyses and is responsible for the production and quality control of all tables, figures and listings.

Adverse events that have met the seriousness criteria defined in the protocol are reported on the serious adverse event (SAE) forms using the MediData RAVE platform. An SAE case report, consisting of the information reported in the SAE forms, subject characteristics documented in the case report forms, and additional source data such as a hospital discharge summary, is recorded in a validated ARGUS database which is managed by Covance. Any discrepancies in critical data fields of each SAE report will be reconciled between the ARGUS and THR-1442-C-476 clinical databases prior to database lock. The SAE coding, analyses and summaries will be based on the final study data recorded in the clinical database. Theracos will perform a review of all tables, figures and listings before final acceptance.

An independent Cardiovascular Endpoint Committee (CEC) has been established to prospectively adjudicate, in a blinded fashion, suspected cardiovascular events. All suspected major adverse cardiovascular events (MACE) reports should also be captured as SAEs and every effort will be made to ensure that events recorded as suspected MACE are coded in a similar manner within the safety database. The SAE listing will also be reviewed periodically by the CEC members to identify potential MACE that may not have been reported by the study investigators.

The independent CEC will receive and adjudicate the following types of events:

- All deaths
- Suspected non-fatal myocardial infarction
- Suspected hospitalization for unstable angina (HUA)
- Suspected transient ischemic attack (TIA) and stroke
- Suspected hospitalization for HF (HF)
- Reported coronary revascularization procedures

For study THR-1442-C-476, MACE+ is defined as adjudicated cardiovascular death, non-fatal myocardial infarction, non-fatal stroke, or hospitalization for unstable angina.

An independent DKA adjudicator is to review, in a blinded fashion, all suspected cases of acidosis to identify confirmed or probable diabetic ketoacidosis (DKA) according to prespecified DKA case definitions.

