4.3. SAFETY ENDPOINTS

The key safety endpoints include:

- A 5-point composite endpoint of CV death, non-fatal myocardial infarction, non-fatal stroke, hospitalization for unstable angina, or coronary revascularization
- A 6-point composite endpoint of CV death, non-fatal myocardial infarction, non-fatal stroke, hospitalization for unstable angina, coronary revascularization or hospitalization for heart failure
- Individual events including all-cause mortality, CV death, fatal and non-fatal myocardial infarction, fatal and non-fatal stroke, hospitalization for unstable angina, hospitalization for CHF, or coronary revascularization. Both first events and total events, taking account of repeat events will be examined
- Change in eGFR from baseline
- Change in UACR from baseline
- Incidence of adverse events of interest. Adverse events of interest including urinary tract infections (UTI), pyelonephritis urosepsis, genital mycotic infections (GMI), diuretic effects including hypovolemia, hypotension episodes, hypoglycemia, hepatotoxicity, fractures, malignancies, hypersensitivity reactions, acid-base disorders including diabetic ketoacidosis, rash, renal failure events, and amputations

Other safety endpoints include:

- Adverse events
- Clinical laboratory events
- Physical examinations
- Vital signs including orthostatic blood pressure
- Use of concomitant medications

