9.3.3.5. Diabetic Ketoacidosis

During the clinical trial period, potential DKA will be monitored by the measurement of urinary ketones and assessment for signs or symptoms of acidosis at each clinic visit. Clinical presentations or laboratory values that suggest acidosis are to be documented in the DKA CRF. A data package of a suspected DKA case will be provided to the blinded DKA adjudicator. A DKA adjudication form will be completed and event assigned to one of the 5 categories by the independent DKA adjudicator based on clinical data and specified case definitions as outlined below.

Table 7. DKA Case Definitions

Case Term	Case Definitions
Confirmed DKA	
 an episode consisting of symptoms of DKA with ketonuria or ketonemia, AND with one or more biochemical findings of acidosis, which responds to fluid replenishment and, if needed, insulin
Probable DKA	
 an episode consisting of moderate or severe symptoms of DKA, which responds to fluid replenishment and, if needed, insulin OR an episode consisting of moderate or severe symptoms of DKA, moderate or large ketonuria and/or ketonemia without one or more biochemical findings of acidosis, which responds to fluid replenishment and/or insulin
Possible DKA	
 an episode consisting of mild to moderate symptoms of DKA, ketosis not measured or ketonuria moderate or less, condition self-managed, resolves with or without change in diabetic medications; OR an episode of 4+ or greater (40 mg/dL or greater) ketonuria with mild symptoms of DKA; OR an episode of 5+ or greater (80 mg/dL or greater) ketonuria without symptoms of DKA
Unlikely DKA	
 an episode consisting of mild symptoms of DKA with urine ketones measured small or negative; or a measurement of moderate (2+) or less ketonuria without symptoms
Indeterminate DKA	
 mild to moderate symptoms of DKA without measurement of ketosis; self-managed and/or self-resolving

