Additional potential DKA cases may be identified by the adjudicator when reviewing serious adverse event listing or programmatically based on AEs of special interest preferred term list which includes relevant acidosis terms in the MedDRA dictionary. A data package will be generated and submitted to the DKA adjudicator prior to study completion and treatment assignment unblinded. All suspected DKA will be presented in a by-subject listing. Events adjudicated to be “Confirmed DKA” and “Probable DKA” will be summarized in the AEs of special interest table.

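### SAP 9.3.3 tabulates Confirmed or Possible DKA, but SAP 9.3.3.5, which it cites, tabulates Confirmed and Probable DKA in the same table

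*Combined protocol and SAP*

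**What the plan says.** Three places in the SAP name a set of adjudicated DKA categories.

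- **SAP 9.3.3 (AE of Special Interest):** "confirmed or possible DKA events (See Section 9.3.3.5) will be summarized in the same AE of special interest table".
- **SAP 9.3.3.5 (Diabetic Ketoacidosis):** "Events adjudicated to be “Confirmed DKA” and “Probable DKA” will be summarized in the AEs of special interest table".
- **SAP 2.1 (Responsibilities):** the blinded adjudicator reviews suspected acidosis cases "to identify confirmed or probable diabetic ketoacidosis (DKA"). This describes the adjudicator's task and is not a rule for the table.

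Table 7, in SAP 9.3.3.5, sets out five categories: Confirmed, Probable, Possible, Unlikely and Indeterminate. One route to Probable is "an episode consisting of moderate or severe symptoms of DKA, which responds to fluid replenishment and, if needed, insulin". One route to Possible is "an episode of 5+ or greater (80 mg/dL or greater) ketonuria without symptoms of DKA".

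SAP 9.3.3 also explains how special-interest events are found. All of them, "except for DKA, cardiovascular events and amputations, will be prospectively identified based on the MedDRA PTs in the AEs log". DKA therefore enters the table through adjudication.

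**The concern.** The two table rules sit in the current SAP text, concern the same table and are joined by a cross-reference, yet they name different categories. A programmer who follows either sentence is following the plan.

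The table reports a listed endpoint. SAP 4.3 puts the incidence of adverse events of interest among the key safety endpoints, and the list includes "acid-base disorders including diabetic ketoacidosis, rash, renal failure events, and amputations". Protocol 9.6.4 plans that the number and percentage of subjects with treatment-emergent events "of special interest will be summarized for each treatment group by type of AE". Because the adjudication category decides which DKA cases are counted, the choice of sentence decides the reported DKA incidence in each arm. If the choice is made after unblinding, it can be made knowing which count looks better.

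**Working it through.** There is no planned figure to reproduce. The check is a comparison of the rules, followed by the algebra of what each one counts.

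**Step 1. Are Probable and Possible really different?** From Table 7:

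| Category | What it requires |
|---|---|
| Probable | Two routes. Both need moderate or severe symptoms and a response to treatment (fluid, insulin or both, depending on the route) |
| Possible | Three routes: mild to moderate symptoms, self-managed, with ketosis unmeasured or ketonuria no more than moderate; ketonuria of 4+ or more with mild symptoms; ketonuria of 5+ or more with no symptoms |

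They are separate categories, and 9.3.3.5 assigns each event to one of the five. Possible can be met by a urine result alone; Probable cannot.

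**Step 2. Which categories does each rule count?**

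| Rule | Categories counted | Number of 5 |
|---|---|---|
| 9.3.3.5 | Confirmed, Probable | 2 |
| 9.3.3, literal | Confirmed, Possible | 2 |
| 9.3.3, read as at least possible | Confirmed, Probable, Possible | 3 |

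The literal reading of 9.3.3 shares only Confirmed with 9.3.3.5. The looser reading contains both of the 9.3.3.5 categories and adds a third. Neither reading matches 9.3.3.5.

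**Step 3. What happens to the count in one arm?** Let C, P and S be the numbers of subjects with Confirmed, Probable and Possible DKA, and assume that each subject falls in one category only.

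- 9.3.3.5: C + P
- 9.3.3, literal: C + S. Difference from 9.3.3.5: (C + S) − (C + P) = S − P
- 9.3.3, loose: C + P + S. Difference: (C + P + S) − (C + P) = S

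The literal reading can move the count up or down. The loose reading can only raise it or leave it unchanged. The counts agree when S = P (literal) or S = 0 (loose). The documents give no values for C, P or S, so the calculation stops here.

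**Step 4. Does the one-category assumption matter?** Adjudication is per event, so a subject with both a Probable and a Possible episode would be counted once under either rule. The differences in subject numbers are then no longer exactly S − P or S. The formulas hold without that assumption if C, P and S count events instead of subjects.

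**The case against.** The strongest reply is that this is a slip which the SAP itself largely resolves. SAP 9.3.3 is an overview that defers to 9.3.3.5; that section holds the case definitions and states the rule with the category names in quotation marks; and SAP 2.1 independently pairs confirmed with probable. A literal 9.3.3 would drop treated moderate or severe episodes while counting symptom-free ketonuria, which is hard to believe was intended. This is persuasive about intent and supports the proposed correction. It does not make the correction unnecessary: the SAP states no order of precedence, and Possible is a valid Table 7 category, so a table built from 9.3.3 would show no visible error.

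Other points on that side:

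- **The counts may coincide.** True, as step 3 shows. The rules can give different counts; they need not.
- **Preferred terms still play a part.** SAP 9.3.3.5 uses a preferred-term list to find further potential cases, but those go to the adjudicator, so adjudication still decides entry to the table.
- **The cases are visible elsewhere.** All suspected DKA is to be listed by subject, listings are sorted by treatment arm (SAP 14.2.5.3), and treatment-emergent events are tabulated by preferred term (SAP 9.3.2). This limits the harm. However, 9.3.3.5 does not say that the listing shows the adjudication category, so a recount from it is not assured, and no listing can say which count was pre-specified.
- **The reach is narrow.** Correct. DKA is one item in a long list of special-interest events, the summary is descriptive, and adjudication is blinded, so the underlying data are unaffected.

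**Conclusion.** The concern holds. The SAP gives two incompatible rules for which adjudicated DKA events enter the special-interest table, and no reading of 9.3.3 brings it into line with 9.3.3.5. Relative to 9.3.3.5, the subject count per arm changes by S − P or by S, assuming one category per subject; size and direction are unknown because no category counts are given.

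The rate per 100 patient-years and the repeat summaries for insulin and sulfonylurea subjects (SAP 9.3.3.1) may be affected too. The heading of that section covers events identified by preferred term, but 9.3.3 puts DKA in the same table. The primary and key secondary analyses and MACE+ are untouched. It should be corrected, but it does not threaten the trial's main conclusions.

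**What to change.** Before unblinding, change possible to probable in the DKA sentence of SAP 9.3.3, so that it matches 9.3.3.5 and agrees with SAP 2.1. Keep the planned by-subject listing of all suspected DKA as it is.

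The cost is one word in the SAP. No new data, adjudication or analysis is needed.
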